7.2.1 Visit 2 (Day 1)

Study staff will contact the participant by phone approximately 24 hours after vaccination to review and document adverse events.

7.2.2 Visit 3 (Day 7)

An in-person visit will be conducted one week after vaccination. Study staff will collect and review the diary card and document adverse events.

7.2.3 Visit 4 (Day 28)

An in-person visit will be conducted 28 days following vaccination. All Unsolicited Adverse Events will be documented. Study staff will also document any new information regarding solicited adverse events with onset up to 7 days following vaccination, such as resolution. The participant will be informed which vaccine they received based on entry into the CRF by an unblinded staff member.

For all participants, 5mL of blood will be collected in an SST tube. For participants in the CMI subset, 3mL of blood for Quantiferon test will be collected in a heparinised tube, and 20mL of blood for PBMC will be collected in a heparinised tube. Blood samples will be kept at room temperature and transferred to the laboratory within 3 hours of collection.

7.2.4 Visit 5 (3 Months)

Study staff will contact the participant by phone and document information on any medically attended AE or SAE.

Study staff will also document any new information regarding unsolicited adverse events with onset up to 28 days following vaccination, such as resolution.

7.2.5 Visit 6 (6 Months)

For all participants, 5mL of blood will be collected in an SST tube. For participants in the CMI subset, 3mL of blood for Quantiferon test will be collected in a heparinised tube, and 20mL of blood for PBMC will be collected in a heparinised tube. Blood samples will be kept at room temperature and transferred to the laboratory within 3 hours of collection.

7.2.6 Visit 7 (12 Months)

For all participants, 5mL of blood will be collected in an SST tube. For participants in the CMI subset, 3mL of blood for Quantiferon test will be collected in a heparinised tube, and 20mL of blood for PBMC

will be collected in a heparinised tube. Blood samples will be kept at room temperature and transferred to the laboratory within 3 hours of collection. Participants who complete the 12-month study period will receive a gift. If they request, results of their tests will be shared and discussed with them by a member of the study team.

7.2.7 Unscheduled visits

If any participant develops symptoms of Covid-19, they will be instructed to contact the Study Team and to get a PCR test at the nearest facility. If the test is positive the Study Team will seek to obtain a specimen for virology, either residual from the specimen that tested positive, or an additional swab once the positive result is known. One month after the positive test a 5ml blood sample will be collected and serum stored for future serological analysis. The participant will otherwise continue with scheduled study visits. The virology sample will be transported for sequencing and analysis by the Microbiological Diagnostic Unit Public Health Laboratory (MDU) in Melbourne. The study team will maintain telephone contact daily with the participant for the course of his/her illness and fully document all telephone calls. With the subject's permission the Team will seek clinical data from the health care providers or hospital in the event that the subject becomes clinically ill.

7.2.8 Withdrawal of consent - participant withdraws from all trial participation

A participant has the right to withdraw from the trial at any time and for any reason and is not obliged to give his or her reasons for doing so. The Investigator may withdraw the participant at any time in the interests of the participants' health and well-being. In addition, the participant may withdraw/be withdrawn for any of the following reasons:

- Administrative decision by the Investigator
- Ineligibility (either arising during the trial or retrospectively, having been overlooked at screening).
- Significant protocol deviation
- Participant non-compliance with study requirements

The reason for withdrawal will be recorded in the CRF. If the participant has an AE at the time of withdrawal, appropriate follow-up visits or medical care will be arranged, with the agreement of the participant, until the AE has resolved, stabilised or a non-trial related causality has been assigned.

If a participant withdraws from the study, storage of samples and data collected before their withdrawal will still be used in the analysis, unless the participant specifically requests otherwise.

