7.2.10 Replacements

Participants who have been randomised and enrolled may NOT be replaced.

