11.2 Population to be analysed

Analysis of this trial is planned on both the intention-to-treat population (ITT), with all participants to be analysed in the group they were randomised to, as well as on the per-protocol (PP) population, consisting of participants who adhered to the study protocol. However, it is expected that withdrawn participants may not have data to contribute at all time points as blood samples may not be collected after the time of their withdrawal.

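### Section 7.2.8 lets vaccinated participants be withdrawn from all follow-up for deviation, non-compliance or late-found ineligibility, allowing avoidable missing ITT outcomes, mainly at 6 and 12 months

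*Combined protocol and SAP*

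**What the plan says.** Section 7.2.8 is headed "Withdrawal of consent - participant withdraws from all trial participation". It first gives the participant's own right to leave and the investigator's power to withdraw someone for health and well-being. It then adds that "the participant may withdraw/be withdrawn for any of the following reasons" and lists four:

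- a choice made by the investigator on administrative grounds
- failure to meet the entry criteria: "Ineligibility (either arising during the trial or retrospectively, having been overlooked at screening"
- departure from the plan, given as "Significant protocol deviation"
- failure to keep to what the study asks, given as "Participant non-compliance with study requirements"

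After withdrawal, the section provides for follow-up of an adverse event present at that time. It provides for no further blood sampling or outcome follow-up. It does keep what has been gathered: "samples and data collected before their withdrawal will still be used in the analysis", unless the participant asks otherwise.

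Section 11.2 plans an ITT analysis "with all participants to be analysed in the group they were randomised to" and a per-protocol analysis of those who adhered. It also expects that withdrawn participants may lack data at some time points. Section 7.2.10 adds "Participants who have been randomised and enrolled may NOT be replaced". Section 5.2.8 refers discontinuation of the intervention to a section 7.5, but section 7 contains only 7.1 and 7.2.

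**The concern.** The intervention is complete at Visit 1, so afterwards there is no treatment to stop. Deviation, non-compliance and late-found ineligibility then bear only on which analysis set a participant belongs to, and section 11.2 already has a per-protocol set for that purpose. Ending participation on these grounds adds nothing to the per-protocol analysis and can remove outcomes from the ITT analysis.

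The loss may be informative. The exclusions in section 4.4.2 include immunosuppressive medication, HIV infection and congenital immune deficiency. A participant found late to meet one of these could plausibly be less likely to reach seroresponse. The documents give no figure for this.

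In a non-inferiority comparison, ITT and per-protocol results are reported together because they can differ. Each deviating participant whose outcome is lost brings the two closer. After day 28 the clinical investigators know the allocation (section 4.1), so a discretionary withdrawal could then depend on arm.

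**Working it through.** **The plan's own figures.** Section 11.1 gives 90% power (95% versus 95%) and 66% power (93% versus 95%) with 100 per group and a 10-point margin. Section 11.3 uses the lower limit of a 95% interval, so one-sided alpha is 0.025. The unpooled normal approximation reproduces both:

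power = Φ[(0.10 − (p_S − p_F)) / SE − 1.96], with SE = √[p_S(1 − p_S)/n + p_F(1 − p_F)/n]

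- 95/95: SE = √(2 × 0.95 × 0.05/100) = 0.0308; 0.10/0.0308 − 1.96 = 1.284; power 90.1%.
- 93/95: SE = √(0.95 × 0.05/100 + 0.93 × 0.07/100) = 0.0336; 0.08/0.0336 − 1.96 = 0.424; power 66.4%.

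These need all 100 per group to be evaluable. The synopsis recruits exactly 100 per group, with no allowance for loss.

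**Cost in power.** The documents give no withdrawal rate, so the losses below are assumed. The formula is the same.

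| Day-28 loss | n per group | 95/95 | 93/95 |
|---|---|---|---|
| 0% | 100 | 90.1% | 66.4% |
| 5% | 95 | 88.5% | 64.2% |
| 10% | 90 | 86.8% | 61.9% |

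This cost is modest. Bias matters more.

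**Bias at day 28.** Take a standard arm at 95% (section 11.1) and a fractional arm exactly at the margin, 95% − 10% = 85%. Any declaration of non-inferiority is then false. The calculation sums exact binomial probabilities over all outcomes with 100 per arm, deletes k non-responders and applies the Newcombe hybrid score interval. Section 11.3 says only that the interval is score-based, so the choice of Newcombe's is an assumption.

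| k deleted | From both arms | From fractional arm only |
|---|---|---|
| 0 | 2.3% | 2.3% |
| 1 | 2.8% | 4.2% |
| 2 | 3.4% | 7.1% |
| 3 | 3.7% | 10.3% |

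At the expected counts, deleting one non-responder from the fractional arm alone moves its rate from 85/100 to 85/99 = 85.9%, about 0.9 points against a 10-point margin. Deleting one from each arm leaves the difference nearly unchanged: 85/99 − 95/99 = −10.1 points.

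Two other both-arm cases give a sense of scale. Losing 1 to 5 participants per arm, unrelated to response, gives about 2.4% to 2.5%. Withdrawing an assumed 6% of non-responders and 2% of responders in each arm gives just under 3% by simulation.

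**Which column suits which period.**

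- Before the day-28 sample, participants and reactogenicity assessors are blinded, and only staff who randomise, draw up and check vaccine know the arm (sections 4.1 and 6.1).
- The day-28 blood is drawn at the visit where the participant learns the allocation (section 7.2.3), and the assay follows collection by up to two or four weeks (section 3.2.1). A withdrawal early enough to lose that sample therefore cannot be based on its result.
- Once taken, the sample is kept. The both-arm column is the better guide for day 28.
- After day 28 the blind is lifted for clinical investigators. The exposed data are the 6- and 12-month immunogenicity samples and SAE collection to 12 months (section 3.2.2). The plan gives no margin or effect size for these, so no comparable error rate can be computed.

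**The case against.** The strongest reply is that the text permits withdrawal but does not require it. No sentence obliges anyone to withdraw a deviator, and section 11.2 says only that samples may be missing. Data from before withdrawal are retained, and nothing removes a withdrawn participant from ITT. Eligibility is checked by a study doctor or nurse before randomisation on the vaccination day (section 7.2.1, Visit 1). With in-person visits only on days 0, 7 and 28, there is little to be non-compliant with before the primary endpoint. Section 11.3 also leaves detailed methods to a separate SAP, which is not part of this text, so the handling of missing outcomes cannot be judged in full.

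All of this stands and limits the weight of the point. Three stronger readings that a reader might infer are not supported:

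- **That sampling stops for every deviator, or that ITT becomes an analysis of the compliant only.** Deviators who are not withdrawn, and those withdrawn after day 28, still contribute day-28 data to ITT and can be left out of per-protocol. The two sets can still differ.
- **That false non-inferiority at day 28 reaches about 10%.** That figure needs three non-responders lost from the fractional arm and none from the standard arm, which blinding to day 28 makes hard to produce.
- **That the no-replacement rule undercuts ITT.** It protects the randomised set; its only relevance is that lost outcomes cannot be made up.

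Permissive wording does not remove the concern. It leaves the loss of outcomes to case-by-case discretion on grounds unrelated to consent or health.

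**Conclusion.** The point holds as an avoidable weakness in follow-up, and it should be fixed. Section 7.2.8 allows outcomes of vaccinated participants to go missing on grounds that the per-protocol set already covers, and section 11 of the protocol states no method for missing outcomes.

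For the day-28 seroresponse comparison the effect is probably small: a rise in false non-inferiority from 2.3% to between 2.8% and 3.7% for one to three non-responders lost from each arm. The one-arm values of 4.2% to 10.3% are an extreme bound. These figures rest on true rates of 85% versus 95%, 100 per arm, the Newcombe interval and assumed numbers of losses.

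The greater exposure is at 6 and 12 months, for immunogenicity and SAEs, where withdrawal decisions can be made with knowledge of the arm. Its size cannot be derived from the documents.

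**What to change.** In section 7.2.8, limit the end of follow-up to withdrawal of consent and the participant's health and well-being. Record administrative decision, significant deviation, non-compliance and late-found ineligibility as possible per-protocol exclusions. State that, with continued consent, these participants keep the scheduled day-28, 6- and 12-month samples and safety follow-up, and that their data enter ITT. Correct the cross-reference in section 5.2.8, and state in section 11 or the separate SAP how missing outcomes are handled.

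The cost is wording, plus a few samples and contacts that are already in the schedule for participants already enrolled.

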7.2.9 Losses to follow-up

A participant will be considered lost to follow-up if he/she fails to return for two consecutive visits and is unable to be contacted by the trial staff. The following action must be taken if a participant fails to return to the clinic for a required trial visit:

- Trial staff will attempt to contact the participant within one week of the missed visit and reschedule the visit.

- Before a participant is deemed lost to follow-up, trial staff will make every effort to regain contact. Three telephone calls will be made, and two emails sent. All contact attempts will be documented in the participants DCF.
- If the participant continues to be unreachable, he/she will be considered to have withdrawn from the trial with a primary reason of lost to follow-up.

7.2.10 Replacements

Participants who have been randomised and enrolled may NOT be replaced.

7.2.11 Trial Closure

The end of the trial is the date of the last assay conducted on the last sample collected.

8 SAFETY MONITORING AND REPORTING

8.1.1 Definitions for use in trials involving investigational medicinal products

Participant-specific adverse events

Adverse events must be assessed to determine each of the following:

1. Seriousness
2. Relatedness (i.e., causal relationship)
3. Expectedness

Adverse Event (AE): Any untoward medical occurrence in a patient or clinical trial participant administered a medicinal product and does not necessarily have a causal relationship with this treatment.

Adverse Reaction (AR): Any untoward and unintended response to an investigational medicinal product related to any dose administered.

Comment: All adverse events judged by either the reporting investigator or the sponsor as having a reasonable possibility of a causal relationship to an investigational medicinal product would qualify as adverse reactions. The expression 'reasonable causal relationship' means to convey, in general, that there is evidence or argument to suggest a causal relationship.

Serious Adverse Event (SAE) / Serious Adverse Reaction (SAR): Any adverse event/adverse reaction that results in death, is life threatening, requires hospitalisation or prolongation of existing hospitalisation, results in persistent or significant disability or incapacity or is a congenital anomaly or birth defect.

Note: Life-threatening refers to an event in which the participant was at risk of death at the time of the event. It does not refer to an event that hypothetically might have caused death if it were more severe. Medical and scientific judgement should be exercised in deciding whether an adverse event/reaction should be classified as serious in other situations. **Important medical events** that are not immediately life-threatening or do not result in death or hospitalisation but may jeopardise the participant or may require intervention to prevent one of the other outcomes listed in this definition should also be considered serious.

Suspected Unexpected Serious Adverse Reaction (SUSAR): An adverse reaction that is both serious and unexpected.

Safety issues (requiring expedited reporting)

The following definitions describe additional safety events that require expedited reporting to stakeholders including the Sponsor, Investigators, HREC, local governance office and TGA:

Significant Safety Issue (SSI): A safety issue that could adversely affect the safety of participants or materially impact the continued ethical acceptability or conduct of the trial.

Comment: An SSI is a new safety issue or validated signal considered by the Sponsor in relation to the investigational medicinal product that requires urgent attention of stakeholders. This may be because of the seriousness and potential impact on the benefit-risk balance of the investigational medicinal product, which could prompt regulatory action and/or changes to the overall conduct of the clinical trial, including the monitoring of safety and/or the administration of the investigational medicinal product.

Urgent Safety Measure (USM): A measure required to be taken in order to eliminate an immediate hazard to a participant's health or safety. Note: This is a type of SSI that can be instigated by either the investigator or sponsor and can be implemented before seeking approval from HRECs or institutions.

8.2 Capturing and eliciting adverse event/reaction information

Participants will be asked to record local and systemic AEs for 7 days (and longer if symptoms persist at day seven, until resolution or stabilisation) following vaccination in the electronic or paper diary card (solicited AEs). Unsolicited AEs All local and systemic AEs occurring in the 28 days following vaccination observed by the Investigator or reported by the participant, whether or not attributed to study medication, will also be recorded in participant diary and CRF.

Serious adverse events (SAE's) will be followed up for the duration of the trial. Adverse events of special interest will be categorised as per CEPI guidelines (1).

Adverse reactions will be reported through the RCH immunisation service and escalated to the Victorian Specialist Immunisation Services.

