3.2.2 Secondary outcomes

Immunogenicity

Functional antibody – All samples at all timepoints will be assayed using the GenScript cPass SARS-CoV-2 Neutralization Antibody detection kit for both WT and Delta variant RBD antigen.

Neutralizing antibody - A fraction of samples (20%) will be assessed using a SARS-CoV-2 microneutralisation assay undertaken at the PDI, Melbourne. Assays will be done at all four timepoints to the WT (vaccine) strain and for 2 Variants of concern.

Cellular immunity - Cellular immunity will be assessed on a subset of 40% of participants, with samples collected at three timepoints: baseline, 28 days, and 12-months post-vaccination as follows:

- *QuantIFERON Human IFN- γ SARS-CoV-2* (Qiagen) will be performed using heparinised whole blood
- Peripheral blood mononuclear cells (PBMCs) will also be isolated by density gradient centrifugation within 12 hours of collection and stored in liquid nitrogen at MCRI. Assays performed will include IFN- γ Elispot, intracellular cytokine assays (flow cytometry) and multiplex cytokine assays.

Safety

- All solicited adverse events (AE) will be collected for 7 days, all unsolicited AE will be collected for 28 days, and all medically attended AE will be collected for 3 months. SAE will be collected throughout the follow up period of 12 months

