7 TRIAL VISITS AND PROCEDURES

7.1 Schedule of assessments

	Visit 1 (day 0)	Visit 2 (day 1)	Visit 3 (day 7)	Visit 4 (day 28)	Visit 5 (3 mths)	Visit 6 (6 mths)	Visit 7 (12 mths)
Timing	Day 0	Day 1	Day 7	Day 28	3 months	6 months	12 months
Visit window			+ 3 days	+ 7 days	+/- 14 days	+/- 14 days	+/- 14 days
Informed consent	X						
Eligibility confirmation	X						
Randomisation	X						

Blood sampling	X			X		X	X
Vaccination	X						
Vital signs	X						
Issue diary card, ruler and thermometer	X						
Collect diary card			X				
Documentation of Solicited AE	X	X	X				
Documentation of unsolicited AE	X	X	X	X			
Documentation of medically attended AE	X	X	X	X	X		
Documentation of SAE	Throughout study period						
Documentation of confirmed COVID-19 infection	Throughout study period						

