7.2 Description of procedures

7.2.1 Visit 1 (Day 0)

Informed consent must be signed by both participant and study doctor or nurse.

Participant eligibility must be confirmed prior to randomisation and on the same date as administration of the investigational product.

Eligibility must be confirmed by a study doctor or study nurse. Randomisation must be completed by the unblinded vaccinator who will document the participant's randomisation number on the enrolment log.

Study staff will administer a Visit 1 questionnaire documenting demographic information, height and weight, dates and type of primary COVID-19 vaccine, any comorbidities and concomitant medication.

The following vital signs will be recorded by a study doctor or study nurse prior to vaccination: temperature, pulse rate, respiratory rate, and blood pressure.

Prior to vaccination, for all participants, 5mL of blood will be collected and processed according to the SOP. CMI participants will have an additional 25ml collected and processed for Quantiferon analysis and PBMC separation and storage.

Following randomisation, the unblinded vaccinator will administer the applicable vaccine to the participant.

The following vital signs will be recorded by a study doctor or study nurse 15 minutes following vaccination: temperature, pulse rate, respiratory rate, and blood pressure.

Study staff will provide participant with reactogenicity diary card and instruct the participant on how to complete the diary card up to and including 7 days following vaccination.

Study staff will provide the participant with a thermometer and ruler and detailed instructions on how to use these for measuring temperature and potential erythema and induration. Study staff will provide the participant with a schedule of visit appointments and instruct the participant on how to contact the study staff in case of any SAE or symptoms suggestive of COVID-19.

Study staff will keep the participant under observation for minimum 15 minutes and document any immediate adverse events.

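### Section 8.2 records 28 days of adverse events in the participant diary, but the visit schedule ends and collects that diary at about day 7

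*Combined protocol and SAP*

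**What the plan says.** Section 3.2.2 sets the collection period as a safety outcome: "all unsolicited AE will be collected for 28 days". Section 8.2 names the record. Events in that period, "whether or not attributed to study medication, will also be recorded in participant diary and CRF". For solicited symptoms, the same section carries the diary past one week where needed: "and longer if symptoms persist at day seven, until resolution or stabilisation". Section 8.3 gives the diary card, electronic or paper, as an example of an AE source document.

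The visit procedures describe a shorter life for the diary. At Visit 1 staff "instruct the participant on how to complete the diary card up to and including 7 days following vaccination". At Visit 3 (day 7), "Study staff will collect and review the diary card and document adverse events". The schedule in 7.1 has one issue row and one row reading "Collect diary card", which the visit text places at Visit 3. That visit has a window of +3 days.

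The next scheduled contact is Visit 4 (day 28, +7 days): "All Unsolicited Adverse Events will be documented". At the 3-month telephone call staff ask about medically attended AEs and SAEs, and "Study staff will also document any new information regarding unsolicited adverse events with onset up to 28 days following vaccination, such as resolution".

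**The concern.** A site cannot follow both sets of instructions. Section 8.2 treats the diary as a four-week record, and 7.1 with the Visit 1 and Visit 3 text treats it as a one-week record that is then handed in. The same tension affects solicited symptoms still present at day 7: 8.2 keeps them in the diary, but the card has gone back to staff.

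If sites follow the schedule, participants have no contemporaneous record for most of the unsolicited-AE period. Section 8.3 asks for onset date, duration and resolution date, and for each episode of an intermittent event. Section 8.4 grades relatedness partly on timing, and 10.1.3 has the DSMB review AEs by relatedness. Mild, brief events and exact onset dates are what participants are most likely to lose when asked weeks later.

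**Working it through.** The plan gives no figure on this point to reproduce. The check sets the sections side by side and then counts days.

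**1. Where the diary is, by section**

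| Section | Diary status |
|---|---|
| 8.2, unsolicited AEs | In use for 28 days |
| 8.2, solicited AEs | 7 days, longer if symptoms persist at day 7 |
| Visit 1 text | Completed through day 7 |
| 7.1 and Visit 3 text | Collected at day 7 (+3) |
| Visit 4 text | Not mentioned |

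**2. One event traced through.** Take a mild unsolicited event starting on day 15 and gone by day 17, with no medical attendance. Section 8.2 puts it in the diary. The participant was told to stop at day 7, and staff have held the card since Visit 3. At Visit 1 participants are told how to contact staff about SAEs or symptoms suggesting COVID-19, and this event is neither. Visit 4 is the first scheduled contact at which it can be recorded. The 3-month call comes later still and is framed as an update on such events.

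**3. Days beyond the diary and Visit 3.** With Visit 3 on day *a*, the uncovered days number 28 − *a*.

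- *a* = 7: 28 − 7 = 21 days; 21/28 = 75%.
- *a* = 10: 28 − 10 = 18 days; 18/28 = 64%.

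The instruction to complete the card stops at day 7 in either case. The lower figure credits Visit 3 itself with covering days 8 to 10.

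**4. Look-back at Visit 4.** For onset on day *d* and Visit 4 on day *v*, look-back = *v* − *d*.

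| Onset day | Visit 4 on day 28 | Visit 4 on day 35 |
|---|---|---|
| 8 | 20 days | 27 days |
| 18 (midpoint of days 8–28) | 10 days | 17 days |
| 28 | 0 days | 7 days |

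If Visit 3 falls on day 7 and onsets are spread evenly over days 8 to 28 (an assumption), the midpoint row is also the mean. If Visit 3 falls on day 10, the earliest onset left to Visit 4 is day 11, with a look-back of 17 to 24 days.

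**5. Effect by arm.** Suppose a proportion *s* of true events is captured, the same in each arm, with no false reports. A true rate *p* is then observed as *s* × *p*. The ratio between arms is unchanged, since *s* cancels. The absolute rates fall, and the absolute difference shrinks by the same factor. The documents give no basis for a value of *s*.

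**The case against.** The strongest reply is that this is a wording slip in 8.2 and that the data do not depend on the diary. Section 8.2 also names the CRF and covers events observed by the investigator or reported by the participant. The schedule documents unsolicited AEs at days 0, 1, 7 and 28. SAEs are followed throughout and medically attended AEs to 3 months. The diary may be electronic, and a Source Document Plan, not among the documents, is to fix the source of each data item. Much of this stands: events have a route into the CRF, and the more consequential ones have several. What it does not supply is any described aid for new, minor events between Visit 3 and Visit 4. That reliance on recall is an inference, because the Visit 4 text does not say how events are elicited.

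Four stronger readings are tempting and should not be drawn.

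- **That the 28-day entries are impossible, or the 28-day rate unobtainable.** Visit 4 documents all unsolicited AEs, and an electronic diary could stay open.
- **That the duration of persisting reactions is lost.** Section 8.2 extends the diary for them, and Visit 4 takes new information on solicited AEs with onset up to day 7, including resolution. The 3-month call does the same for unsolicited AEs.
- **That the dose comparison is biased.** Participants and those assessing reactogenicity are blinded for 28 days, so capture that differs by arm is unlikely, and 11.3 describes no between-arm test of unsolicited AEs.
- **That day 7 of the reactogenicity record is lost, so Visit 3 must start on day 8.** At most the rest of one day is missed when Visit 3 falls on day 7, and Visit 4 can pick up solicited events with onset up to day 7. Moving the window would be a preference.

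**Conclusion.** The contradiction is in the text and should be corrected. For non-serious, non-medically-attended events starting after Visit 3, the record appears to rest on Visit 4 alone. This leaves 64% to 75% of the collection days without the diary that 8.2 calls for. The 75% and 27-day figures are upper ends: the first needs Visit 3 on day 7, and the second also needs onset on day 8 and Visit 4 on day 35.

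The likely consequence is some under-capture of mild, short events and less accurate onset dates, in a secondary safety outcome. The size cannot be estimated from the documents. The effect is probably similar across arms, provided blinding holds until events have been elicited at Visit 4. The antibody outcome is not affected. The conclusion assumes that no other document issues a diary or memory aid for days 8 to 28.

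**What to change.** Reconcile 8.2 with 7.1 and with the Visit 1 and Visit 3 procedures, in one of two ways:

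- review the card at Visit 3 and leave it, or the electronic diary, with the participant; or
- keep the first card at Visit 3 and issue a second, to run to Visit 4, for unsolicited AEs and solicited symptoms not yet resolved.

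In either case, change the Visit 1 instruction to match and add a "Collect diary card" mark at Visit 4 in the schedule.

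The cost is one extra card or a longer electronic diary period, an edit to the schedule, slightly more burden for participants and some non-return at Visit 4. Deleting the diary from the 28-day sentence in 8.2 would also remove the contradiction, at no cost, but would leave minor events after Visit 3 without a contemporaneous record.
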